5.3 Primary Safety Endpoint

The primary safety endpoint is hospitalization for major bleeding. Bleeding events include intracranial hemorrhage, GI bleeding, bleeding in other locations, or a control of bleeding procedure. To qualify as a major bleeding event, there also must be documented evidence of a blood product transfusion within +/- 7 days of the bleed.

6 Identification of Endpoints

The method for identification of clinical endpoints is documented in the protocol. Endpoints were identified through electronic sources (including EHR [PCORnet CDM], CMS claims or private insurance claims data) or patient reported via the patient portal (see figure below). Confirmation by electronic data is required for patient reported clinical endpoints. Some clinical endpoints, based on patient-reported events that could not be confirmed or refuted by the data sources listed above, were confirmed through medical record review.

For endpoints based on a hospitalization for a specific reason (MI, stroke, bleeding), the primary analysis will include endpoints identified by diagnostic codes both (a) in the principal position, and (b) for which the position is unknown. In the CMS and private insurance claims data, diagnostic code position for inpatient encounters is usually known, and we will use all codes reported. In the PCORnet EHR data, most, but not all, sites consistently use the principal/secondary designation for diagnoses. When diagnosis position is unavailable for a specific code, its position is recorded as "Other/Unknown" in the PCORnet CDM. Therefore, in the PCORnet data, when diagnosis position is available, only codes in the principal position will be used; but when diagnosis position is unavailable, all codes will be used. This requirement will ensure that we do not exclude events from sites that do not record this information. We will use diagnosis codes known to be (and designated as) secondary in sensitivity analyses only. More details on endpoint extraction are contained in the Query Technical Specifications.

Sensitivity analyses, including analyses addressing potential misclassification in endpoint definitions, are described in Section 7.10.

7 Summary of Statistical Methods

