To assess impact of under-reporting due to participants moving or seeking care outside of the CDM health system, we will repeat the primary analysis modifying the censoring rules for CDM data such that the censoring date will be the last date the patient encountered the health system. This will include inpatient and outpatient visits, labs, vitals and prescription medication fills. All other censoring dates will remain the same.

Under the assumption that under-reporting is non-differential between treatment groups, the impact on primary analysis inference would be a loss of power. If the primary result is non-significant then we will assess overall impact of under-reporting, by performing a tipping point analysis to identify how many events would have to be missed to achieve significance. We will take an approach that is adapted and simplified from that described by Little et al (2016) for a sensitivity analysis for missing data. A Weibull model of the primary endpoint will be fit to the entire ITT population, with independent variables including an indicator that participant is at risk for under-reporting (Scenarios 1, 2, 3 and 6 in the table) and selected baseline characteristics. Other independent variables may be considered. Events will be sequentially added for those participants at risk of under-reporting across treatment groups. For each increment, *i* events will be imputed from the Weibull model 1000 times. A Cox model as specified for the primary analysis will be fit to the resulting dataset and treatment effect hazard ratio will be estimated, with standard errors adjusted using standard multiple imputation combining rules. The increment will be increased until the upper limit of the 95% CI for the HR of the treatment effect crosses 1.0.

To assess impact of misclassification of electronic phenotype definitions, we will repeat the primary analysis modifying the code-based definitions of primary endpoints to include codes in 1) principal position only and 2) any position.

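### SAP section 6 applies the diagnosis-position rule to each EHR code, so an Other/Unknown MI, stroke or bleeding code can count as the reason for admission even when another code in the same stay is flagged principal

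*SAP*

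**What the plan says.** For MI, stroke and bleeding, SAP section 6 states that "the primary analysis will include endpoints identified by diagnostic codes both (a) in the principal position, and (b) for which the position is unknown". For the EHR data it explains that "most, but not all, sites consistently use the principal/secondary designation for diagnoses". It then defines missing position at the level of the code: "When diagnosis position is unavailable for a specific code, its position is recorded as" Other/Unknown. The working rule is that "when diagnosis position is available, only codes in the principal position will be used; but when diagnosis position is unavailable, all codes will be used". The reason given is about sites: "This requirement will ensure that we do not exclude events from sites that do not record this information". Designated secondary codes are held back: "We will use diagnosis codes known to be (and designated as) secondary in sensitivity analyses only". Further detail sits in a separate document: "More details on endpoint extraction are contained in the Query Technical Specifications".

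The protocol leaves this decision to the SAP. Sections III.E.4.b, III.E.4.c and III.E.4.e give priority to the principal position and say that the SAP will settle how far secondary and unknown positions are used.

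SAP section 7.10 repeats the primary analysis with the code definitions changed "to include codes in 1) principal position only and 2) any position". It adds a tipping-point analysis in which positive and negative predictive value each run from 0 to 1.

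**The concern.** These endpoints are hospitalizations for a stated reason, which is why the SAP keeps designated secondary codes out of the primary analysis. If one code in a stay is flagged principal, a different code in that stay marked Other/Unknown is probably not the reason for admission. In substance it resembles a secondary code, yet it enters the primary analysis because of its label.

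Little downstream would catch such an event. Under protocol III.E.4, a hospitalization that meets the coding algorithm in an electronic source needs no further confirmation. SAP 5.1 says the validation results will not feed into the primary analyses. For bleeding, SAP 5.3 also requires a transfusion within 7 days either side. That is a real filter, but a weaker one in surgical stays, where transfusion may have other causes.

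At stake are a diluted hazard ratio for the primary effectiveness and safety endpoints, which in a comparison of two doses favours a finding of no difference, and overstated cumulative event rates.

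**Working it through.** **Step 1: which codes each rule admits (EHR data)**

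| Endpoint code in the stay | SAP 6 as written | Encounter-level rule | Principal-only (7.10) | Any position (7.10) |
|---|---|---|---|---|
| A. Flagged principal | counts | counts | no change: counts | counts |
| B. Flagged secondary | no | no | no | counts |
| C. Other/Unknown, no code in the stay flagged principal | counts | counts | no | counts |
| D. Other/Unknown, another code flagged principal | counts | no | no | counts |

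Row C is what the stated reason calls for. Row D is the excess. Going from the primary definition to principal-only removes C and D together, so a change in the result cannot be assigned to D. Going to any position adds only B. The predictive-value grid is not tied to code position. None of the three isolates row D.

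**Step 2: the plan's own power figures**

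Inputs from SAP 7.6: 1322 primary events with a 15% relative risk reduction (HR 0.85), stated power 88%; 642 safety events with a 20% reduction (HR 0.80), stated power 81%; two-sided alpha 0.05; equal arms.

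Schoenfeld: power = Φ(|ln HR| × √D / 2 − 1.96).

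- Primary: 0.1625 × 36.36 / 2 − 1.96 = 0.995, so 84.0%. The stated 88% is not reproduced from 1322 events; it would need about 1489. This point does not depend on that gap, and 84.0% is the baseline below.
- Safety: 0.2231 × 25.34 / 2 − 1.96 = 0.867, so 80.7%, which agrees with the stated 81%.

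**Step 3: illustrative dilution**

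The documents give no count of row D events and no share of them that is false. Assume that a share f of all counted events is false, equal in number in the two arms and unrelated to dose, and that the true events stay at the planned totals.

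With x = f(1 + HR) / (2(1 − f)), the observed HR is (HR + x) / (1 + x), and counted events are D / (1 − f).

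Example, primary, f = 0.05: x = 0.05 × 1.85 / 1.90 = 0.0487; observed HR = 0.8987 / 1.0487 = 0.857; counted events = 1322 / 0.95 = 1392; power 82.1%.

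| Assumed f | Primary HR | Primary events | Primary power | Safety HR | Safety events | Safety power |
|---|---|---|---|---|---|---|
| 0 | 0.850 | 1322 | 84.0% | 0.800 | 642 | 80.7% |
| 2% | 0.853 | 1349 | 83.3% | 0.804 | 655 | 79.9% |
| 5% | 0.857 | 1392 | 82.1% | 0.809 | 676 | 78.6% |
| 10% | 0.864 | 1469 | 80.0% | 0.818 | 713 | 76.4% |

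Counted events, and so crude event rates, rise by the factor 1 / (1 − f): about 2% at f = 2% and 5% at f = 5%. If the counted total were instead held at 1322, so that false events displaced true ones, primary power would be 82.5% and 80.1% at those two shares. Adding to the true events fits a looser rule better.

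**The case against.** The strongest reply is that an ambiguity is not a demonstrated error. No passage shows a stay with both a flagged principal code and an Other/Unknown endpoint code. The operative sentence, followed directly by a reason about sites, can be read at site or encounter level. The Query Technical Specifications, which are not among the documents, may already contain an encounter check. This stands, and it is why the point is only that the wording permits such events. It does not remove the need for a sentence: the protocol assigns the decision to the SAP, and two programmers could build different endpoints from the present text.

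A reader might go further and infer that false events are in fact entering the primary analyses. The documents do not support that. An Other/Unknown code beside another principal diagnosis may record a true MI, stroke or bleed, including one that prompted the admission but was flagged differently. For bleeding, the transfusion requirement removes some doubtful cases.

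A reader might also infer that the principal-only analysis is worthless, because sites that never record position can contribute no EHR hospitalization event to it. That is too strong. If the loss is unrelated to dose, as SAP 7.10 assumes for reporting errors, it lowers event rates and precision but leaves the hazard ratio essentially unbiased. Those participants still contribute deaths, claims events and confirmed self-reports. The encounter-level definition also lies between the principal-only and primary definitions, so close agreement of those two hazard ratios would answer much of the concern. Disagreement would leave the source unknown.

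Finally, the predictive-value grid spans any false share one might assume, under the same equal-between-arms assumption. It shows what misclassification could do in general, not how much this rule contributes.

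**Conclusion.** The point holds as a gap in the written rule. SAP section 6 works on the individual code, has no encounter-level condition, reaches further than its stated purpose, and is inconsistent with its own handling of designated secondary codes.

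The actual size is unknown. Under the assumptions in Step 3, a 2% to 5% false share moves a primary hazard ratio of 0.85 to about 0.853 to 0.857 and costs roughly 1 to 2 points of power (84.0% to 83.3% or 82.1%). For safety, the same shares move 0.80 to 0.804 to 0.809, with power falling from 80.7% to 79.9% or 78.6%; this is approximate, since SAP 7.4 plans a Fine and Gray analysis. The direction, toward 1, rests on the SAP's assumption that errors are non-differential. At these shares the effect on inference is modest. The case for the change is that the endpoint would be defined unambiguously at very little cost.

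**What to change.** 1. Add one sentence to SAP section 6: in EHR data, Other/Unknown codes are used only when no code in the encounter is flagged principal. If the Query Technical Specifications already say so, cite that text instead.
2. Report, by arm and for each endpoint, the number of events that depend on an Other/Unknown code beside a recorded principal diagnosis (row D). This replaces the assumed shares above with a count.
3. Optionally, when event rates from the principal-only analysis are reported, note the sites that never record position, or restrict EHR-based follow-up to sites that do.

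The cost is a sentence, a change to the query logic if no such check exists, and one small table; no new data are needed. The downside is that a few true events whose stay carries a mis-flagged principal code would leave the primary analysis. They would remain in the any-position sensitivity analysis.

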7.1 Baseline Demographics and Medical History

Descriptive summaries of baseline demographic and clinical variables will be generated for each randomized treatment arm of the study. Continuous baseline variables will be presented as medians with 25th and 75th percentiles, and discrete variables will be summarized using frequencies and percentages.

Patient age, sex, current smoking status, race and ethnicity are reported in the patient portal data as well as in CDM. These characteristics will be summarized from the patient portal data.

Medical history data obtained from CDM includes: atrial fibrillation, prior coronary revascularization, hypertension, coronary artery disease, congestive heart failure, prior MI, diabetes, COPD/Asthma, chronic kidney disease, peripheral artery disease, prior smoking, significant bleeding disorder, cerebrovascular disease, significant GI bleed, intracranial hemorrhage, and peptic ulcer. Comorbidities are identified through ICD 9 and ICD 10 diagnosis and procedure codes and CPT codes in any care setting at any time during the lookback period. The lookback period is 5 years prior to trial enrollment. Codes can be used from any diagnosis position (principal, secondary or other/unknown).

Medical history information obtained from the CDM is limited to diagnosis and procedures codes associated with encounters within the lookback period that occurred in the recruiting site's healthcare system. There is no expectation that codes associated with older or out-of-system encounters will be captured. This is a standard limitation of EHR data.

7.2 Populations for Analysis

The Intent-To-Treat (ITT) Population will consist of all patients randomized to a treatment group in the study regardless of their compliance with the study medication. For all ITT analyses, participants will be analyzed as randomized.

Patients who were inappropriately randomized due to administrative errors (excluding those taking prohibited medications) were withdrawn from the study prior to initiating study drug. These patients were included in the randomization scheme, but will have no study data beyond that and will not be included in the ITT population.

Given the pragmatic nature of the trial and the expected gaps in data on patient compliance with randomized dose, we will not define the per-protocol (PP) population. Sensitivity analyses are described in section 7.10 that address treatment compliance.

7.3 Primary Effectiveness Comparison

The primary endpoint of this study will be event-free survival from the first event of a composite of all-cause death, hospitalization for nonfatal myocardial infarction, or hospitalization for nonfatal stroke. The primary effectiveness analysis will be performed in the ITT population based on randomized treatment assignment. Event-free survival rates will be compared using Cox proportional-hazards models, equivalent to the log-rank test, using censoring rules described in Section 7.5. The test will be two-tailed and will be performed at an overall α of 0.05. The proportional hazards assumption will be checked for the randomized treatment assignment using weighted Schoenfeld residuals. If there is evidence of non-proportionality, a cautious interpretation of the Cox model hazard ratio will be encouraged, and non-parametric event rate estimates will be emphasized (see below).

In addition to Cox regression, cumulative endpoint event rates will be estimated as a function of follow-up time in each treatment group using Kalbfleisch & Prentice's nonparametric estimator of the cumulative incidence function (CIF). The Kalbfleisch & Prentice CIF estimator is equivalent to the Kaplan-Meier estimator when applied to endpoints that are not subject to competing risks. Cumulative endpoint event rates and differences in cumulative endpoint event rates will be

estimated and presented with 95% confidence intervals. These non-parametric analyses are important for descriptive purposes and will be a focus of interpretation if the event rate curves cross. They may also be used to construct summary measures of treatment effect which are interpretable when the proportional hazards assumption is violated.

Sensitivity analyses for potential misclassification and under-reporting of endpoints and for nonadherence to randomized aspirin dose are described in Section 7.10. An additional sensitivity analysis will be performed to take clustering of patients within sites into account, using the robust sandwich covariance estimator.

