Patients who are identified as candidates for the trial will be directed to the ADAPTABLE patient portal for the eConsent as well as an abbreviated eligibility confirmation prior to randomization. The ADAPTABLE patient portal will include the electronic patient consent (eConsent) that satisfies the local IRB and state law requirements of the participating CDRNs and HRPN. CDRN personnel will be available, if needed, to give a more local perspective on protocol-related consultations. For patients without internet access, patient consent via the ADAPTABLE patient portal will be obtained during a process facilitated by site research staff during clinic encounters, and follow-up will be done via telephone contact with the DCRI Call Center.

Patients will be randomized via the patient portal in a 1:1 ratio to receive 81 mg vs 325 mg of aspirin. Patients will be asked to obtain their randomized aspirin dose at their local pharmacies. The randomization scheme will be established before the inception of enrollment. In a trial of this size, stratified randomization has no significant advantages.

After randomization, during the early first web portal contact or telephone contact (for patients without internet access) from 1 to 3 weeks after randomization, patients will be asked to answer questions related to current aspirin use and dose and other specific concomitant medications. They will also be asked to provide contact information such as their name, email and home address, phone numbers, and

contact information for a family member or friend not living with them. These data will be used to contact patients who miss multiple visits and to identify events such as hospitalizations that occur out of network. The enrolling sites will be responsible for ensuring that randomized patients complete their early first contact visit (1-3 weeks after randomization).

Neither patients nor healthcare providers will be blinded to their treatment assignment, as blinding would add substantial complexity and cost without commensurate incremental benefit. The "hard" outcomes, large sample size, and equipoise in the clinical community should enable valid results to be obtained, and we have no reason to believe that investigator or clinician bias will play a role in ascertainment or classification of events.

III.C.3. Concomitant Therapy

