These data will be analyzed, and the trial statistician will provide them to the DSMB regularly. The DSMB will review the data every 6 months and recommend any necessary changes to the conduct of the trial. Given that aspirin has been used for more than a century and most SAEs have been reported in conjunction with its use, the rate of unsuspected SAEs that the sites will/can submit through MedWatch to the FDA is expected to be very low.

III.F. Summary of Statistical Methods

III.F.1. Baseline Demographic, Clinical, Functional, and Procedural Characteristics

Descriptive summaries of baseline demographic and clinical variables will be generated for each randomized treatment arm of the study. Continuous baseline variables will be presented as medians with 25th and 75th percentiles, and discrete variables will be summarized using frequencies and percentages.

III.F.2. Populations for Analysis

The ITT population will consist of all patients randomized to a treatment group in the study regardless of their compliance with the study medication. For all analyzed using the ITT population, participants will be analyzed as randomized.

The per-protocol population is a subset of the ITT population, excluding participants who complied with the randomized treatment for less than 50% of the follow-up or had major protocol deviations expected to affect the primary effectiveness or safety endpoint.

III.F.3. Primary Effectiveness Comparison

The primary endpoint of this study will be survival free from the first event of a composite of all-cause death, hospitalization for nonfatal MI, or hospitalization for nonfatal stroke. Specifications for the identification of these endpoints are provided in **Section III.A.5.** The primary effectiveness analysis will be performed by the ITT principle based on randomized treatment assignment. Event-free survival rates will be compared using Cox proportional-hazards models. ⁹⁶ In the absence of any other covariates, this is the same as the log-rank test. ⁹⁰ The test will be 2-tailed and will be performed at an overall alpha of 0.05.

III.F.4. Primary Safety Comparison

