The DSMB may recommend stopping the trial for any safety-related concern at any time. Particular attention will be paid to all-cause mortality. For effectiveness, the trial will compare doses of aspirin that have been proven effective in previous trials, and thus it is unlikely that any dramatic differences will appear early. However, the DSMB will monitor these differences about every 6 months over the 3.5 years of the trial. Thus, we anticipate 6 interim analyses and 1 final analysis. Because there are multiple tests, each test must be made at an adjusted alpha level using group sequential-testing methods. To minimize the chance of stopping early due to a spurious result, the endpoints will be tested at the planned analyses using a specific method known as the Haybittle-Peto rule. 101 This rule tests the

endpoints at the 0.001 level (z = 3.29, two-sided) at each interim review and then makes the final test at the 0.0499 level (z = 1.9605). Thus, there is only minimal penalty for interim analyses.

The decision-making structure and process for the DSMB will be described in a separate DSMB charter.

III.G.6. Data Auditing Conventions

Data will be collected via the study patient portal (Sections III.A.3.c and III.A.3.h).

IV. Human Subjects

IV.A. Protection of Human Subjects

IV.A.1. Sources of Data

Data obtained from the study participant web portal, from the CDM, from Centers for Medicare Services, and from HealthCore/Anthem Research Network, an HPRN, will be transferred to the DCRI along with unique participant identifiers. Details for the process and authorization for Medicare and health plan data linkages are contained in a separate Linkage Plan document. Data contained within the CDM will be obtained from each of the recruiting sites and the HPRN and will be transferred to the DCRI. The control of access to databases at DCRI will be managed centrally by the DCRI through user passwords linked to appropriate access privileges. This protects data from unauthorized view and modifications as well as inadvertent loss or damage. Within the secondary SAS databases, UNIX group access control will be used for maintaining similar security. The Sun workstation login will be secured by extensive user password facilities under UNIX.

IV.A.2. Potential Risks

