7.6 Power

Calculations were performed using PASS software. For the primary effectiveness endpoint, power calculations were based on an estimated primary event rate of 5.5% per year (in the higher risk arm), annualized rate of loss to follow-up of 5%, two-sided significance level α of 0.05, 7,500 patients in each treatment arm, enrollment of 38 months and a maximum follow-up period of 44 months. The power of the chosen testing strategy to detect a statistically significant

difference under these assumptions is 85% if the relative risk reduction is 15%, corresponding to a total of 1246 primary effectiveness events.

In November 2019, the DSMB approved extended follow-up in response to updated power calculations based on observed primary event rates. Assuming 7,500 patients in each treatment arm, annualized rate of loss to follow-up of 5%, two-sided significance level α of 0.05, enrollment of 38 months and maximum follow-up period extended to 50 months, the power to detect a relative risk reduction of 15% is 88% when the overall primary event rate is 4.5% in the higher risk arm, corresponding to a total of 1322 primary effectiveness events.

For the primary safety endpoint, power calculations were based on an estimated primary event rate of 2.5% per year (in the higher risk arm), annualized rate of loss to follow-up of 5%, two-sided significance level α of 0.05, 7,500 patients in each treatment arm, enrollment of 38 months and a maximum follow-up period of 44 months. The power of the chosen testing strategy to detect a statistically significant difference under these assumptions is 81% if the relative risk reduction is 20%, corresponding to a total of 642 primary safety events.

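### The primary Cox model omits baseline risk factors the trial already collects; the test is valid, but adjustment would add roughly 0.6 to 4.7 points of power under assumed prognostic strengths

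*SAP*

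**What the plan says.** SAP 7.3 specifies the primary comparison this way: "Event-free survival rates will be compared using Cox proportional-hazards models, equivalent to the log-rank test". Protocol III.F.3 makes the absence of covariates explicit: "In the absence of any other covariates, this is the same as the log-rank test". On level and sidedness, SAP 7.3 says: "The test will be two-tailed and will be performed at an overall α of 0.05".

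The design does not balance on prognosis by stratification either. Protocol III.C.2 states: "In a trial of this size, stratified randomization has no significant advantages".

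The data for adjustment exist. SAP 7.1 says: "Patient age, sex, current smoking status, race and ethnicity are reported in the patient portal data as well as in CDM". It also lists medical history taken from the Common Data Model (CDM), including diabetes, chronic kidney disease, heart failure, prior MI, and peripheral and cerebrovascular disease. Protocol III.B uses age, diabetes, smoking, creatinine, heart failure, and cerebrovascular and peripheral arterial disease as enrichment factors for higher risk.

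The further analyses of the primary endpoint in SAP 7.3, 7.8, 7.9.2 and 7.10 cover site clustering, a 10-day landmark, withdrawal of consent, reported aspirin dose as a time-varying covariate, COVID-19 censoring, Bayesian models, under-reporting and misclassification. None is a treatment comparison adjusted for baseline risk.

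On power, SAP 7.6 states that "the power to detect a relative risk reduction of 15% is 88" per cent, "corresponding to a total of 1322 primary effectiveness events". Protocol III.F.5 gives the same pair of figures.

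**The concern.** When patients differ widely in baseline risk, a treatment-only Cox model estimates a hazard ratio closer to 1 than the ratio that holds among patients of equal risk, with almost the same standard error. Its test statistic is therefore smaller than that of a model including the risk factors. The difference is information given up, and it can be recovered without more patients or longer follow-up.

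This matters here for two reasons. Follow-up has already been extended to 50 months in response to updated power calculations (SAP 7.6). And the stated event count supports somewhat less power than the documents say.

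**Working it through.** **1. The plan's own power figure.** Inputs: 1322 events, a 15% reduction taken as hazard ratio 0.85, 1:1 allocation, two-sided 0.05 (SAP 7.3 and 7.6; Protocol III.F.5).

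Schoenfeld: z = |ln 0.85| × √1322 / 2 = 0.16252 × 36.359 / 2 = 2.9545.

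Power = Φ(2.9545 − 1.96) = Φ(0.9945) = 84.0%.

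The final-look level of 0.0499 in Protocol III.G.5 also gives 84.0%, and Freedman's formula gives 83.8%. Power of 88% would need 4 × (1.96 + 1.175)² / 0.16252², about 1,489 events. So the stated 88% is not reproduced. The same formula gives 80.7% for the SAP's safety scenario (642 events, ratio 0.80; stated 81%) and matches Protocol Table 7 to within about one point. I use 84.0% as the base.

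**2. Information lost by leaving out baseline risk.** The documents give no hazard ratio, C-index or risk spread for any baseline variable, so the standard deviation s of the baseline log-risk score is an assumption. The model:

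- hazard = λ · exp(sX + βA), with X standard normal, A the arm, and exp(β) = 0.85 within risk level;
- administrative follow-up uniform from 12 to 50 months (38 months' accrual), 5% annual loss to follow-up, and λ set to give 1322 events.

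Numerical integration gives the hazard ratio exp(β*) that the treatment-only Cox model estimates. The variance is close to 4/1322 with or without adjustment, so the loss is L ≈ 1 − (β*/β)².

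| s | approx. C-index, Φ(s/√2) | treatment-only HR | L |
|---|---|---|---|
| 0.4 | 0.61 | 0.8512 | 1.8% |
| 0.6 | 0.66 | 0.8530 | 4.3% |
| 0.8 | 0.71 | 0.8557 | 8.0% |
| 1.0 | 0.76 | 0.8595 | 13.2% |

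Example, s = 0.8: ln 0.8557 / ln 0.85 = 0.1558 / 0.1625 = 0.959, and 1 − 0.959² = 8.0%. Using the log-rank score instead of the Cox estimate gives 1.6%, 4.0%, 7.8% and 13.0%. In 500 simulated trials each at s = 0.6, 0.8 and 1.0, the losses were 4.5%, 7.5% and 13.4%.

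**3. Power after adjustment.** The plan's 15% reduction is set from annualized rates in each arm, so I take 0.85 as the marginal ratio and hold unadjusted power at 84.0%. The loss is practically unchanged on that footing. Adjusted power = Φ(2.9545 / √(1 − L) − 1.96), and the equivalent extra events are 1322/(1 − L) − 1322.

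| s | adjusted power | gain over 84.0% | equivalent extra events |
|---|---|---|---|
| 0.4 | 84.6% | 0.6 points | 24 |
| 0.6 | 85.5% | 1.5 points | 59 |
| 0.8 | 86.9% | 2.9 points | 115 |
| 1.0 | 88.7% | 4.7 points | 201 |

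On this footing the conditional hazard ratio runs from just under 0.85 at s = 0.4 to about 0.840 at s = 1.0, a shift of about 0.001 to 0.010.

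**The case against.** **The unadjusted test is valid and its target is legitimate.** This stands. A reader might infer that the treatment-only estimate is biased. It is not: the marginal and conditional hazard ratios are different quantities, and a pragmatic trial of a dosing policy may reasonably want the marginal one. If the true marginal ratio is 0.85, unadjusted power stays at 84.0% however varied the patients' risk. The point is only that another valid test would have more power.

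**The size of the gain is unknown.** This also stands. A reader might infer a fixed and sizeable loss, since the enrichment factors are familiar risk markers. The documents list them without any measure of strength. Everyone enrolled has atherosclerotic disease and at least one enrichment factor, which may narrow the spread of risk. The calculation also adjusts for the exact score that generates the events. In practice, six of the nine candidate covariates come from CDM codes, which SAP 7.1 limits to a five-year lookback within the recruiting health system. Incomplete capture moves the gain toward the rows with smaller s. It does not bias the comparison, because history recorded before enrolment cannot depend on the assigned dose.

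**The plan does use these variables.** A reader might infer that baseline risk is ignored throughout. It is not. Protocol III.B uses it for enrichment, SAP 7.11 enters subgroup variables one at a time in interaction models, and SAP 7.9.2 and 7.10 put unnamed baseline characteristics into Weibull imputation models. None of these adjusts the primary comparison.

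**The 84% against 88% mismatch is a separate matter.** Agreed. A reader might infer that adjustment repairs it. Only the s = 1.0 row reaches 88%, and the stated figures would still need reconciling, as would the higher-risk-arm rate attached to them: 4.6% in the Protocol III.F.5 text, 4.5% in Table 6 and in SAP 7.6.

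**Conclusion.** The point holds as a minor matter of efficiency. The primary model contains treatment only, no baseline-adjusted version is planned, and the needed variables are already collected and largely treated by the protocol as prognostic. For an assumed log-risk standard deviation between 0.4 and 1.0, the information lost is about 2% to 13%, and adjustment adds about 0.6 to 4.7 points to a recomputed 84.0%. Each figure is an upper bound for its standard deviation. Weak or poorly captured covariates would leave a gain of under one point. The conclusion rests on a normal risk score, a constant treatment effect across risk levels, exponential event times, and the stated accrual, follow-up and loss to follow-up. It does not show that the planned analysis is wrong or that its type I error is affected.

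**What to change.** Before results by arm are seen, amend SAP 7.3 so that the primary Cox model adjusts for a short, named list:

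- from the portal: age (continuous), sex and current smoking;
- from the CDM, coded as in SAP 7.1: diabetes, chronic kidney disease, heart failure, prior MI, peripheral artery disease and cerebrovascular disease.

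Treat an uncoded condition as absent, and state a simple rule for missing portal values that ignores treatment arm, so that no randomized patient drops out of the analysis. Report the unadjusted hazard ratio and log-rank p-value beside the adjusted result. The same list could replace the unnamed baseline characteristics in SAP 7.9.2 and 7.10. If results by arm have already been seen, keep the planned test as primary and add the adjusted model as a labelled supportive analysis.

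The cost is SAP wording, covariate coding and the missing-value rule; no new data are needed. The downside is that the primary hazard ratio becomes conditional on the covariates and differs slightly from the marginal one. The unadjusted hazard ratio and the cumulative-incidence differences already planned in SAP 7.3 still show the marginal effect.
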